3.1 Research Design Outline

The study aims to perform a randomized control trial on CAI participants in INTI physiotherapy centre and compare with healthy controls as a causal comparative study

Study 1 (Formerly titled “Effect of short duration video assisted mindful deep breathing among collegiate athletes with chronic ankle instability – a Randomised Control Trial”) involves participants with chronic ankle instability by using the Cumberland Ankle Instability Tool (CAIT)¹⁰, if the score was ≤ 27 in the CAIT tool over 30 by fulfilling the inclusion criteria.

Study 2 is a causal comparative study, which involves age matched healthy collegiate athlete from local university and compared them with the baseline parameters of Study 1.

The proposed study designs are all investigator blinded in the randomized control trials (Study 1). Participants only be involved in Study 1 and baseline measurements are compared with Study 2.

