3.6 Assessment & Outcomes Measures

Study 1

Chronic ankle Instability (CAI) participants will be assessed for:

1. Primary outcomes
 - Cumberland Ankle Instability Tool (CAIT)
 - Ankle stability will be assessed by validated 9-item Questionnaire, to find the chronic ankle disability score among participants and to recruit in the study if the score was ≤ 27 in the CAIT tool over 30.
 - Y-balance test (YBT)
 - The dynamic balance of the participants will be assessed using reliable and validated the Y balance test (YBT) by measuring the distance in anterior, posterolateral, and posteromedial directions.
 - Visual analog scale (VAS)
 - CAI participants pain intensity will be record by self-reported pain intensity on a 10 cm line to point out the pain level. The point at 0 cm represents "no pain" and 10 cm represents "worst pain".
 - Brief Pain Inventory (BPI)

- Besides VAS, pain intensity and pain interference will be recorded using 4-items (worst pain, least pain, average pain, and pain right now) to measure the pain intensity, and 7-items (general activity, mood, walking, normal work, relations, sleep, enjoyment of life) to assess the pain interference. The participants will be instructed to report the pain intensity from 0 (no pain) to 10 (as pain bad as you can imagine). Similarly, the pain interference is recorded from 0 (does not interfere) to 10 (completely interferes)
- Mindful Attention Awareness Scale (MAAS)
 - CAI participants will be assessed by 15-item questionnaire to identify the participants' mindfulness level during the ankle instability.
- Oxford Happiness Questionnaire (OHQ)
 - Happiness level of CAI participants will be assessed using the Oxford Happiness Questionnaire (OHQ), which consists of a 29-item questionnaire.
- Functional ankle disability index (FADI)
 - CAI participants will be asked to complete 34-item questionnaire used to check the participant's general daily activity and sports specific functions for physical function and disability.

2. Secondary outcomes

- Non-invasive wireless electroencephalogram (EEG)
 - EEG will be used at 14 positions: AF3, AF4, F3, F4, F7, F8, FC5, FC6, P7, P8, T7, T8, O1, and O2. The EEG recordings of the CAI participants will be collected between 9 and 12 hours in the morning to reduce participants sleeping artifacts and to exclude the EEG from the influence of circadian variables. The EEG recordings will be recorded in eyes closed and eyes

open for 2mins.

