The time commitment required of participants for assessment will be approximately 60 mins.

Study 2

Healthy control participants will be assessed for:

1. Primary outcomes

- Cumberland Ankle Instability Tool (CAIT)
 - Ankle stability will be assessed by validated 9-item Questionnaire, among participants and to recruit in the study if the score was >27 in the CAIT tool over 30.
- Functional ankle disability index (FADI)
 - Participants will be asked to complete 34-item questionnaire used to check the participant's general daily activity and sports specific functions for physical function.
- Mindful Attention Awareness Scale (MAAS)
 - Participants will be assessed by 15-item questionnaire to know the mindfulness attention level.
- Oxford Happiness Questionnaire (OHQ)
 - Happiness level of participants will be assessed using the Oxford Happiness Questionnaire (OHQ), which consists of a 29-item questionnaire.

2. Secondary outcomes

- Non-invasive wireless electroencephalogram (EEG)

- EEG will be used at 14 positions: AF3, AF4, F3, F4, F7, F8, FC5, FC6, P7, P8, T7, T8, O1, and O2. The EEG recordings of the participants will be collected between 9 and 12 hours in the morning to reduce participants sleeping artifacts and to exclude the EEG from the influence of circadian variables. The EEG recordings will be recorded in eyes closed and eyes open for 2mins.

The time commitment required of participants for assessment will be approximately 45 mins.

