3.7 Sample Size

Study 1

G*power was utilized for sample size calculation with equal group sizes (i.e ratio of groups 1:1). A total of 36 participants with CAI (i.e. 18 in each group) to be able to reject the null hypothesis that the population means of the experimental and control groups are equal with probability (power) 0.95. The Type I error probability associated with this test of this null hypothesis is 0.05¹¹.

- Assuming a total drop-out rate of 10%, we will recruit 20 subjects for each group, i.e. 20 experimental and 20 experimental control group.

Study 2

A total of 20 participants without CAI will be recruited and compared with the age matched CAI participants in the study 1.

4. Statistical Analysis Plan (SAP)

All Studies

Descriptive and inferential statistics will be used. Normally distributed data will be presented by mean and standard deviation (SD) and non-normally distributed data will be presented by median and interquartile range. Categorical data will be presented using percentages. SPSS (version 22.0) will be used for all statistical analyses.

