4.1 Primary Outcomes

Study 1

The primary analyses will compare: (1) experimental vs experimental control group guidelines on their mean and standard deviation: (i) pain score (VAS & BPI), (ii) balance scores (CAIT & FADI), (iii) mindful attention (MAAS), and (iv) happiness scores (OHQ). Comparisons will be made using an unpaired t-test or a Mann-Whitney test for parametric and non-parametric data, respectively. P-values <0.05 will be considered statistically significant.

2*4-Repeated measures analysis of variance (ANOVA) will be performed to test the significant difference in the intervention effects between the time intervals (baseline, mid-intervention, post-intervention, and follow-up) and also between the two groups (Experimental control group and Experimental Group).

The post-hoc analysis will be conducted to investigate significant effect within the time intervals. Condition on if the sphericity violated (p-value < 0.05), the Greenhouse- Geisser estimated correction will be applied.

Effect sizes for will be calculated using Cohen's d (d) with 95% confidence intervals (95%CI) using the 'effsize' package¹². Effect sizes will be considered small if $0.2 \leq d < 0.5$, medium if $0.5 \leq d < 0.8$, and large if $d \geq 0.8$.

Study 2

The primary analyses will compare: (1) CAI participants vs healthy control group guidelines on their mean and standard deviation: (i) balance scores (CAIT &FADI) (ii), mindful attention (MAAS) and (iii) happiness scores (OHQ). Comparisons will be made using an unpaired t-test or a Mann-Whitney test for parametric and non-parametric data, respectively. P-values <0.05 will be considered statistically significant.

Effect sizes for will be calculated using Cohen's d (d) with 95% confidence intervals (95%CI) using the 'effsize' package¹². Effect sizes will be considered small if $0.2 \leq d < 0.5$, medium if $0.5 \leq d < 0.8$, and large if $d \geq 0.8$.

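### Study 2 tests CAIT as a primary outcome between groups that were selected on CAIT, so the p-value only restates the entry rule

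*Protocol*

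**What the plan says.** Section 3.6 uses CAIT to admit participants to both studies. For Study 1 the rule is "to recruit in the study if the score was ≤ 27 in the CAIT tool over 30". For Study 2 it is "to recruit in the study if the score was >27 in the CAIT tool over 30", and this rule sits in the bullet that names CAIT as the first of four Study 2 primary outcomes (CAIT, FADI, MAAS, OHQ).

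Section 3.1 says of the healthy athletes that the study "compared them with the baseline parameters of Study 1", so the CAI scores entering Study 2 are those taken before treatment.

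Section 4.1, Study 2, then sets the primary comparison as "CAI participants vs healthy control group guidelines on their mean and standard deviation: (i) balance scores (CAIT &FADI"), followed by MAAS and OHQ. The method is given as "Comparisons will be made using an unpaired t-test or a Mann-Whitney test for parametric and non-parametric data, respectively", with the criterion "P-values <0.05 will be considered statistically significant". Cohen's d with a 95% confidence interval follows, graded small from 0.2, medium from 0.5 and large from 0.8. Nothing in the protocol confines CAIT in Study 2 to describing the groups.

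**The concern.** A group comparison can inform only if the data could have come out either way. Here the recruitment rule places every CAI participant on one side of a CAIT threshold and every control on the other. The null hypothesis of equal CAIT is excluded before anyone is measured. A small p-value would confirm that the eligibility rule was applied and nothing more, and Cohen's d would be inflated by the gap that the rule creates.

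At stake is how Study 2 reads. One of its four primary outcomes would come out as highly significant with a large effect, and could be taken as evidence about ankle stability in athletes with CAI when it repeats the definition of the groups.

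**Working it through.** **Inputs from the protocol**
- CAI entry: CAIT at most 27 of 30 (3.1 and 3.6, Study 1).
- Control entry: CAIT above 27 of 30 (3.6, Study 2).
- Time point: Study 1 baseline (3.1).
- Controls: 20 (3.7: "A total of 20 participants without CAI will be recruited and compared with the age matched CAI participants in the study 1").
- CAI participants: 20 per arm, 40 in all (3.7: "Assuming a total drop-out rate of 10%, we will recruit 20 subjects for each group").

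**Assumptions**
- Scores are whole numbers, the entry score is the baseline score, and tests are two-sided.
- Section 3.7 does not say whether all 40 CAI participants or an age-matched subset enter Study 2, so 40 versus 20 and 20 versus 20 are both shown.

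The protocol gives no power calculation for Study 2, so there is no planned figure to reproduce.

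**Step 1: ranges.** CAI scores lie in 0–27 and control scores in 28–30. Every control exceeds every CAI participant.

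**Step 2: Mann-Whitney under complete separation.** U = 0 for any data that satisfy the entry rules. Without ties,

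z = (n1·n2/2) / √(n1·n2·(n1+n2+1)/12).

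| n (CAI vs control) | Numerator | Denominator | z | p, normal approximation | p with continuity correction | Exact p = 2/C(n1+n2, n1) |
|---|---|---|---|---|---|---|
| 40 vs 20 | 400 | √(40·20·61/12) = 63.77 | 6.27 | 3.6e-10 | 3.7e-10 | 4.8e-16 |
| 20 vs 20 | 200 | √(20·20·41/12) = 36.97 | 5.41 | 6.3e-8 | 6.8e-8 | 1.5e-11 |

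Tied scores shrink the denominator, so the approximate p-values are smaller still when ties occur.

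**Step 3: selection alone, with no real difference between populations.** One homogeneous population was generated, split at 27/28, and tested as planned. The score distributions are assumed, since the protocol gives none.

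| Assumed CAIT population | n | Runs per setting | p<0.05 | Median d |
|---|---|---|---|---|
| Normal, mean 25–27.5, SD 1.5–5, rounded, capped at 30 (four settings) | 40 vs 20 | 5,000 | 100% | 2.4 to 2.9 (smallest seen 1.6) |
| Uniform 0–30; uniform 24–30; normal mean 27.5, SD 2 | 40 vs 20 and 20 vs 20 | 1,000 | 100%, both tests | 2.3 to 3.6 |

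In the second set the largest p seen was 8.4e-7. An outcome unrelated to the selection was significant in 4% to 6% of the same runs, close to the nominal 5%.

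**Step 4: can the t-test escape?** A search over patterns with one-sided outliers found only an extreme case. With 39 CAI scores of 27, one of 0, and all 20 controls at 28:
- CAI mean = 39·27/40 = 26.325, so the difference is 1.675.
- Pooled SD = 3.50, so d = 1.675/3.50 = 0.48.
- t = 0.478·√(40·20/60) = 1.75 on 58 df, p = 0.086.

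These data are grossly non-normal, so the plan's own rule sends them to Mann-Whitney, where p is about 4e-14.

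**Step 5: what if CAIT were measured again after screening?** With an assumed reliability of 0.6, 0.8 or 0.9, Mann-Whitney at 40 versus 20 was still significant in 96%, 100% and 100% of runs.

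**The case against.** The strongest defence is that the harm is contained. Study 2 is a non-randomised baseline comparison, its 20 controls rest on no calculation involving CAIT, and no gatekeeping or alpha sharing lets the CAIT result affect the FADI, MAAS or OHQ tests. The randomised Study 1 comparison of CAIT between arms is untouched. All of this is true, and it limits the importance of the point. It does not make the test informative. Nor does the protocol present CAIT as a mere check that the groups differ: it is a named primary outcome with a significance criterion and a graded effect size.

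Three qualifications stand:
- Significance is strictly guaranteed only for Mann-Whitney on the entry scores. For the t-test, or for scores taken again later, it is practically certain. A large d is likewise practically certain, not guaranteed.
- It is the p-value that carries no information. CAIT means and SDs still show how far below the cut-off the CAI sample lies. Cohen's d is inflated by the selection but not fixed by it: with CAI scores truncated at 27, moving the assumed population from mean 22, SD 6 to mean 12, SD 5 raised the median d from about 2.4 to about 4.3.
- FADI is not an entry criterion, but it measures ankle function, and section 3.2 seeks controls without CAI or musculoskeletal injury. It may partly reflect the same selection.

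**Conclusion.** The concern holds. As written, the Study 2 test of CAIT checks the recruitment rule and not a hypothesis. Complete separation gives p of about 4e-10 at 40 versus 20 and about 7e-8 at 20 versus 20 by the normal approximation. Selection from a single population is enough to produce a median d of 2.3 to 3.6, far above the protocol's own threshold of 0.8 for a large effect.

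The p-values rest only on the entry rules, the group sizes and reuse of the entry score as baseline. The values of d also rest on assumed score distributions, though the conclusion was the same in every one tried. The point affects one of four Study 2 primary outcomes and should be corrected; it does not touch Study 1.

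**What to change.** In section 3.6, Study 2, move CAIT out of the primary outcomes and state it as the eligibility criterion and a group descriptor. In section 4.1, Study 2, remove CAIT from the hypothesis tests and from the Cohen's d calculation, and report it for each group by mean and SD, or median and interquartile range, without a p-value. Keep FADI, MAAS and OHQ as the tested primary outcomes, with a sentence noting that a FADI difference may partly follow from how the groups were chosen. It would also help to say whether all 40 CAI participants or an age-matched subset enter the comparison.

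The cost is wording in two sections. CAIT is still collected for eligibility, no visit or sample size changes, and no informative result is lost.

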4.2. Secondary Outcomes

Study 1

The primary analyses will compare: (1) experimental vs experimental control guidelines on their mean and standard deviation of brain waves (alpha, beta, theta, gamma and delta).

Comparisons will be made using an unpaired t-test or a Mann-Whitney test for parametric and non-parametric data, respectively. P-values <0.05 will be considered statistically significant.

2×4-Repeated measures analysis of variance (ANOVA) will be performed to test the significant difference in the intervention effects between the time intervals (baseline, mid-intervention, post-intervention, and follow-up) and also between the two groups (Experimental control group and Experimental Group).

The post-hoc analysis will be conducted to investigate significant effect within the time intervals. Condition on if the sphericity violated (p-value < 0.05), the Greenhouse- Geisser estimated correction will be applied.

Effect sizes for will be calculated using Cohen's d (d) with 95% confidence intervals (95%CI) using the 'effsize' package. Effect sizes will be considered small if $0.2 \leq d < 0.5$, medium if $0.5 \leq d < 0.8$, and large if $d \geq 0.8$.

Study 2

The primary analyses will compare: (1) CAI participants vs healthy control group guidelines on their mean and standard deviation brain waves (alpha, beta, theta, gamma and delta).

Comparisons will be made using an unpaired t-test or a Mann-Whitney test for parametric and non-parametric data, respectively. P-values <0.05 will be considered statistically

significant.

Effect sizes for will be calculated using Cohen's d (d) with 95% confidence intervals (95%CI) using the 'effsize' package. Effect sizes will be considered small if $0.2 \leq d < 0.5$, medium if $0.5 \leq d < 0.8$, and large if $d \geq 0.8$.

Pearson's correlation or a spearman's correlation for parametric and non-parametric data, respectively will be used to report the association of EEG with the primary outcomes pain intensity (VAS &BPI) and pain interference (BPI).

4.3 Missing Data

For participants who are randomized and do not attend for assessment, a mean imputation of the assessment scores from their allocation group will used.

5. Informed Consent Forms (ICF)

Study 1

Written consent will be gained from the study participants with CAI using the consent forms attached to the application.

Study 2

Written consent will be gained from the study participants without CAI using the consent forms attached to the application.

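### Filling missed assessments with the arm mean and analysing them as observed data makes a nominal 5% test run at about 8% at the planned 10% drop-out, and about 12% if drop-out reached 20%

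*Protocol*

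**What the plan says.** Section 4.3 of the protocol gives the whole missing-data rule: "For participants who are randomized and do not attend for assessment, a mean imputation of the assessment scores from their allocation group will used". It sits under the protocol's own section 4, the statistical analysis plan, so the method is fixed here and not left to another document.

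Section 4.1 sets the analyses that will use the completed data. For two-group comparisons: "Comparisons will be made using an unpaired t-test or a Mann-Whitney test for parametric and non-parametric data, respectively". For the repeated assessments: "2*4-Repeated measures analysis of variance (ANOVA) will be performed to test the significant difference in the intervention effects between the time intervals". The threshold is "P-values <0.05 will be considered statistically significant", and Cohen's d is to be reported with 95% confidence intervals. Section 4.2 repeats this for the EEG outcomes. Neither section, nor 4.3, mentions a variance correction, reduced degrees of freedom, multiple imputation or a sensitivity analysis.

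Section 3.7 expects the rule to be needed: "Assuming a total drop-out rate of 10%, we will recruit 20 subjects for each group". Section 3.5 schedules post-baseline assessments at weeks 3, 6 and 12.

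**The concern.** Giving each non-attender the mean of his or her own arm leaves the arm mean and the within-arm sum of squares exactly where they were, but the software counts the filled-in value as another observation. The standard deviation is divided by too many degrees of freedom and the standard error by too large a sample. Both are understated, always in the direction of false positives.

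The rule also discards what is known about the absent participant, namely the baseline score and any earlier visits, and credits that person with the average result of those who stayed.

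Section 3.7 raises recruitment from 18 to 20 per arm so that about 18 remain evaluable after drop-out. Section 4.3 then analyses 20 as though all had been observed, which undoes that reasoning. The same inflation affects every primary and secondary outcome with missed assessments. Cohen's d, which the plan grades against fixed cut-offs, is inflated too.

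**Working it through.** **Inputs from the protocol.** Type I error 0.05 (3.7; sidedness not stated, taken as two-sided). 18 evaluable and 20 recruited per arm, 10% drop-out (3.7). Unpaired t-test or Mann-Whitney, and 2x4 ANOVA (4.1). Arm-mean imputation (4.3). No effect size or SD is given, and none is needed, because the rejection rate under the null does not depend on scale.

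**Assumptions.** Data missing completely at random; the imputed mean is that of the same arm at the same visit. Drop-out of 20% and 30% are sensitivity values that are not in the protocol.

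**The plan's own figures.** 18 / (1 − 0.10) = 20 per arm and 36 / 0.90 = 40 in total, as stated. With 20 + 20 complete observations the t-test on 38 degrees of freedom has a Type I error of exactly 5.0%.

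**Effect of the rule on the t-test.** Let n = 20 be the number counted per arm, m the number observed per arm, and SS the pooled within-arm sum of squares.

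- Valid SE: sqrt[SS / (2(m − 1))] × sqrt(2/m), on 2m − 2 degrees of freedom.
- Reported SE: sqrt[SS / (2(n − 1))] × sqrt(2/n), referred to 38 degrees of freedom.
- Ratio r = sqrt[(m − 1)/(n − 1)] × sqrt(m/n).
- The reported test rejects when |t| on 2m − 2 degrees of freedom exceeds 2.024 × r, where 2.024 is the 97.5% point of t on 38 degrees of freedom.

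For m = 18: r = sqrt(17/19) × sqrt(18/20) = 0.897. The effective cut-off is 2.024 × 0.897 = 1.817, and P(|t on 34 df| > 1.817) = 0.078.

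| Imputed per arm | r | Type I error | 95% CI coverage |
|---|---|---|---|
| 0 | 1.000 | 5.0% | 95.0% |
| 1 | 0.949 | 6.3% | 93.7% |
| 2 (planned 10%) | 0.897 | 7.8% | 92.2% |
| 4 (20%, assumed) | 0.795 | 11.8% | 88.2% |
| 6 (30%, assumed) | 0.692 | 17.3% | 82.7% |

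A simulation of 100,000 runs gave 7.77% for 2 per arm. Letting the number missing vary at random around 10% or 20% gives 8.0% and 12.2%. Unequal splits with the same total missing give 7.9% to 8.0% and 12.1% to 13.0%.

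**Mann-Whitney.** By simulation, about 9% with 2 per arm imputed and about 15% to 16% with 4. Tied imputed values make it worse than the t-test.

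**2x4 ANOVA, group-by-time test (simulation).** With 1, 2 and 2 missing per arm at weeks 3, 6 and 12, about 7.5%; with 2, 4 and 4, about 10% to 11% (within-person correlation 0.5 and 0.7). With the Greenhouse-Geisser correction and correlation 0.5, the rates are 7.6% (2 per arm) and 11.3% (4 per arm) if every post-baseline visit is missed, and about 5.8% and 7.4% if only the last is missed.

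**Cohen's d.** The SD shrinks by sqrt(17/19) = 0.946 with 2 per arm, so d is about 6% too large (1/0.946 = 1.057). With 4 per arm it shrinks by sqrt(15/19) = 0.889, so d is about 13% too large. At the planned drop-out an observed d of 0.76 would be reported as 0.76/0.946 = 0.80 and move from the plan's medium class to its large class.

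**Observed data only.** The t-test on 18 + 18 (34 df) or 16 + 16 (30 df) runs at 5.0%.

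**The case against.** The strongest reply is about scope. The 7.8% belongs to one case: the t-test at one visit, 2 per arm imputed, data missing completely at random. If the 10% is cumulative to week 12, earlier visits have fewer imputed values, and 1 per arm gives 6.3%. The ANOVA interaction may be as low as about 5.8%. Only 10% drop-out is in the protocol. Section 4.3 also does not say whether the mean is visit-specific, or whether one missed visit triggers the rule. All of this is fair and limits the size of the error, but every scenario examined with missing data still exceeds 5%, and Mann-Whitney is worse than the headline.

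A second reply concerns bias. If 20% of an arm drop out and truly score 0.5 SD worse (an assumption), that arm's mean is overstated by 0.20 × 0.5 = 0.10 SD. A simple analysis of observed data would have the same bias, since imputing the arm mean does not move it. This stands: the fault specific to the rule is the understated variance. A mixed model reduces such bias only so far as baseline and earlier visits predict the missing scores.

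A third reply is that dropping imputation and keeping the planned t-test already restores 5.0%, so a mixed model is more than the minimum. That is true under the same assumptions. The mixed model is still preferable because it uses the partial data of participants who miss a visit.

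**Conclusion.** The concern holds. Followed as written, the plan gives standard errors that are too small and a Type I error above the 0.05 it states. At the planned 10% drop-out the single-visit t-test runs at 7.8%, with 92.2% coverage; at an assumed 20% it runs at 11.8%, with 88.2% coverage. The t-test figures are exact for 20 per arm, equal missingness, data missing completely at random and same-visit arm means. The ANOVA and Mann-Whitney figures are from simulation, and the ANOVA figures also rest on an assumed within-person correlation. The error always favours a positive finding, and the plan expects the drop-out that triggers it. The rule needs to be changed before any data are analysed.

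**What to change.** Delete the mean-imputation rule in section 4.3. Analyse all randomised participants with a mixed model for repeated measures on the observed data: group, visit, group-by-visit interaction, baseline score as covariate, unstructured covariance. SPSS fits this. If a completed data set is wanted, use multiple imputation within arm from baseline and earlier visits, combined by Rubin's rules, as a sensitivity analysis. Any t-test or Mann-Whitney comparison that is kept should use observed values only, and Cohen's d should use the observed SD.

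The cost is one rewritten paragraph in 4.3, matching edits to 4.1 and 4.2, and a different SPSS procedure, with no extra participants or assessments. Removing imputation alone widens the standard error by about 11% at 10% missing (1/0.897 = 1.114) and 26% at 20% (1/0.795 = 1.258). The baseline covariate gives some of this back: at an assumed correlation of 0.5 it multiplies the standard error by sqrt(1 − 0.25) = 0.866, and 1.114 × 0.866 = 0.97. At the planned drop-out, valid intervals need then be no wider than those the present rule would report.
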